5.1. Mortality Study - All Communities

5.1.1. Core Elements

We will conduct the following study activities for the mortality study:

Training

Standardization activities before each biannual census will consist of didactic classroom instruction and mock census activities, followed by in-field training.

Pre-census and mapping questionnaire

Before the beginning of the study, we will perform a pre-census to be able to list all compounds and household in our study area. This pre-census will help us organize our data census collection by knowing the area we will be working on.

The pre-census will include all questions ask during regular census (see chapter census below) and will include a mapping questionnaire about the characteristics of each household:

- Wall, roof and ground of the house
- Type of water supply
- Latrinization
- Electricity
- Telephone (if exist take number with permission)
- Cooking
- Education of the head of household and mother/guardian
- Child individual information:
 - o Pre schooling
 - o Breastfeeding
 - o Use of bednet
 - o Handicap

Census

An enumerated population census for 0 – 60 month olds (focusing on this age group) will be conducted every 6 months by trained field workers masked to study arm, recording births, deaths, and migration of children eligible for treatment. Pregnant

women will be noted at each census, to maximize inclusion of newborns on the subsequent census.

Core Census Elements

The following elements will be considered part of the core HDSS census activities:

- Enumeration of the compound
- Full enumeration of household members with emphasis on children aged 0-60 months (age, sex) in a way that each child could be linked to his mother
- Enumeration of pregnancies
- Recording of caregiver for each child <60 months
- Recording head of household
- Mid-upper arm circumference measurement for all children aged 0-60 months
- GPS coordinates

Random Census Verification

A repeat census will be conducted in a random selection of households at each study visit. Personnel will be different from the original census. This will allow us to assess whether the census identified all births, deaths, and migratory episodes relative to the previous census.

Verbal Autopsy

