2.1 Planned Analyses

2.1.1 Mortality Trial

The primary prespecified analysis will use the number of deaths in each community as the outcome variable. For analysis, a death is counted when an individual in the target age range 1–59 months is enumerated as alive on census i ($i = 0, 1, 2, 3$) and is not on census $i + 1$ due to death. Census i takes place at the beginning of the study, and each subsequent census takes place approximately six months later.

Primary Analysis.

The primary analysis will be conducted as **negative binomial regression**. The number of person-years (for persons in the target age range) is derived by summing the person-times for each period. The community-level predictor consists of treatment arm for the community. Specifically, the treatment variable is a community level variable, not an individual level variable. The statistical significance assessed by permutation testing at the level of the randomization unit.

Individuals who are in the target age range at the beginning of any study period, but who are no longer in the target age range by the end, are considered to be fully enrolled and contribute the full amount of person-time for that period.

The analysis will be **two-sided**, with a **type I error rate** (alpha) of 0.05.

Statistical considerations.

- Statistical tests will be conducted with Monte Carlo permutation based on the randomization unit. The number of replications will be 10,000, unless the Monte Carlo confidence interval for the P-value includes 0.05. In this case, 10,000,000 will be used, and this fact reported.
- Tests for interaction by age sub-groups and by phase on the additive scale will be conducted to evaluate for statistically significant subgroup differences.
- Model adequacy will be checked by examination of residuals or other goodness of fit tests as needed. Inadequate model fit will prompt us to report alternative models.
- For negative binomial regression, an aggregation parameter of 30 or greater will cause us to re-fit using Poisson regression.
- Multiple imputation will be used in case of missing baseline covariates (if applicable). Missing outcome variables will be handled by sensitivity analysis and reporting of conditional results.

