2.2 Interim Monitoring

Efficacy. The trial is designed specifically to collect three years of data, because of

interest in whether the treatment effect is durable after the first. However, in case of a large effect found after one year, it may be desirable to expand treatment to all communities.

A single interim analysis conducted at alpha of 0.001 will be conducted. Specifically, the interim analysis will be conducted when mortality data are available for the first year (two study periods).

The final analysis would be conducted at alpha 0.049.

Futility. An interim analysis of futility is proposed, to be finalized in consultation with the Data and Safety Monitoring Board. Specifically, we propose to conduct negative binomial regression on village-level mortality counts comparing the treatment and control arms (using a common aggregation parameter) using only data from the first year. This analysis will be conducted using simulation. We suggest consideration of the conditional power to detect a 30% effect. If this drops below 20% at the interim analysis, discontinuation of the trial or other changes to the protocol may be made in consultation with the Data and Safety Monitoring Board.

Interim analysis will be executed by the trial biostatistician at the central site.

3 Sample Size Considerations

We use the following formula (cited from [?]):

$$c = 1 + (z_{\alpha/2} + z_{\beta})^2 \frac{(\lambda_0 + \lambda_1)/y + k^2(\lambda_0^2 + \lambda_1^2)}{(\lambda_0 - \lambda_1)^2}$$

where

c is the number of clusters per arm,

y is the number of person-years per cluster,

λ_0 is the rate in the control group,

λ_1 is the rate in the treatment group,

k is the coefficient of variation in both groups,

α is the alpha level,

β and is the type II error rate.

- The base rate for mortality is assumed to be 0.02 per year in the target age range.
- We assume the same coefficient of variation for village-level mortality as for the Niger site, i.e. 0.34.
- We assume that 16.7% of the population is in the target range of 1–59 months.
- We assume an average community size of 1000 people.
- We assume 10% loss to follow-up per year.
- The effect size is 0.1365.

The number of clusters per arm for Burkina Faso is 170, and the total number of clusters for Burkina Faso is 340.

The sample size is fixed at 341 clusters at the begining of the study.

We estimate that 341 clusters will provide 80% power to detect a 13.65% reduction in mortality in 1-59 month age group.

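### The primary mortality model adjusts for nothing, although about half of the planned variance lies between communities and age and MUAC are recorded everywhere before the first dose

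*SAP*

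**What the plan says.** SAP 2.1.1 makes the number of deaths per community the outcome, with person-years as the denominator, and takes the P-value from permutation at the randomization unit. On predictors it says only: "The community-level predictor consists of treatment arm for the community". The one supplementary mortality model, a Cox regression, names no covariate either. A line on multiple imputation of missing baseline covariates applies only if there are any, and it names none. The only covariate-adjusted mortality analysis is a secondary individual-level Poisson model with age.

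Protocol 5.1.1, which covers all communities, lists among the core census items "Mid-upper arm circumference measurement for all children aged 0-60 months", together with each child's age and sex and household GPS. A pre-census questionnaire adds housing, water, latrines, education, breastfeeding and bednet use. Protocol 6.1 (Census Timing) requires the census to be locked for a household before treatment is given there. SAP 2.1.1 confirms that MUAC is available in all 341 communities. SAP 4 stratifies randomization by HDSS membership (48 of the 341).

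On variance and power, SAP 3 says: "We assume the same coefficient of variation for village-level mortality as for the Niger site, i.e. 0.34"; and "We estimate that 341 clusters will provide 80% power to detect a 13.65% reduction in mortality in 1-59 month age group".

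**The concern.** In a community-randomized trial, the uncertainty in the arm comparison comes from Poisson variation in the death counts and from real differences in mortality between communities. Covariates measured before treatment can reduce the second part if they predict community mortality. Protocol Chapter 2 names malnutrition and young age as drivers of child deaths, so community mean MUAC and age mix are natural candidates. The number of communities is fixed and the design has no power to spare. A plan that ignores these data may accept a wider primary interval than it needs.

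**Working it through.** **Inputs (SAP 3 unless stated).** Control rate λ0 = 0.02 per person-year. "The effect size is 0.1365", so λ1 = 0.02 × (1 − 0.1365) = 0.01727. k = 0.34. Communities average 1000 people with 16.7% in the age range, which gives 167 children. Loss is 10% per year and follow-up is three years (SAP 2.2). Two-sided alpha is 0.05 (SAP 2.1.1).

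The SAP does not state person-years per community, y. I take y = 167 × 3 × 0.9 = 450.9. The alternative 167 × (1 + 0.9 + 0.81) = 452.6 gives almost the same results.

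**Reproducing the plan's figure.** The SAP's formula is c = 1 + (z_α/2 + z_β)² × V / (λ0 − λ1)², where V = (λ0 + λ1)/y + k²(λ0² + λ1²).

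- Poisson part: 0.03727 / 450.9 = 8.27 × 10⁻⁵
- Between-community part: 0.1156 × 0.00069825 = 8.07 × 10⁻⁵
- V = 16.34 × 10⁻⁵, and (λ0 − λ1)² = 7.453 × 10⁻⁶
- c = 1 + 7.849 × 21.92 = 173.1 per arm (172.7 with y = 452.6)

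The SAP says "The number of clusters per arm for Burkina Faso is 170", so its figure reproduces to within 2%. At 170.5 per arm, power is Φ(√(169.5 / 21.92) − 1.960) = Φ(0.821) = 79.4%, against the stated 80%. For the last look the SAP says "The final analysis would be conducted at alpha 0.049", which gives 79.2%.

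**Between-community share.** 8.07 / 16.34 = 49.4%. It is 47 to 52% for the main three-year person-time variants (y = 407 to 501). With two years and 10% loss it would be 39%, but then c = 216.6, far from the SAP's 170.

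**Effect of adjustment.** Let R² be the share of between-community variance that the covariates explain, and replace k² by k²(1 − R²). The documents give no R², so the range is assumed.

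| R² (assumed) | Power, 341 communities | Detectable reduction at 80% power | Interval narrower by | Unadjusted communities for the same power |
|---|---|---|---|---|
| 0 | 79.4% | 13.75% | 0 | 341 |
| 0.1 | 81.4% | 13.4% | 2.5% | 359 |
| 0.2 | 83.4% | 13.1% | 5.1% | 378 |
| 0.3 | 85.4% | 12.7% | 7.7% | 400 |

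The narrowing is 1 − √(1 − 0.494 R²). Each 0.05 of R² adds about one point of power.

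**Simulation check.** Negative binomial models were fitted to 341 simulated communities with log-normal rates (1,500 runs per setting, simulation error about 1 point, Wald test). Unadjusted and adjusted power were 78.9 and 80.2% at R² = 0.1, 81.5 and 84.1% at 0.2, and 79.7 and 86.1% at 0.3. This agrees with the formula.

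**If the number of communities is 278.** Protocol Chapter 3 gives 278 communities where the SAP gives 341. At 139 per arm, power is 70.9% unadjusted and 75.3% at R² = 0.2.

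**The case against.** The strongest reply is that nothing here is wrong. An unadjusted rate ratio with permutation inference is valid, the trial was sized for it, and it is easy to compare with the earlier trial that this one sets out to confirm. That stands. It is why the unadjusted ratio should be kept and why this is a point about precision.

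The second reply is that the benefit is not shown. Protocol Chapter 2 says that malnutrition and young age matter for children; it does not say that community means predict community rates. This also stands. A reader might infer that the plan certainly throws power away, but the documents give no R², and the gain could be close to zero.

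A reader might also expect chance differences in age mix to guarantee some gain. They do not. Month-0 infants leave that age group within a year, while deaths accrue over three years in a population that is listed afresh every six months. Simulating this with infants dying at 2 to 8 times the rate of older children (assumed), chance variation in month-0 infant share explains at most about 0.3% of the between-community variance. Lasting differences in fertility could add more, but the documents have no data on them.

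Distance to the nearest health facility looks like another ready covariate. Household GPS is collected, but no section records facility coordinates, so it cannot be counted as available.

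Third, adjustment may change what is estimated. Under a log link, the adjusted and unadjusted rate ratios share an estimand only if the rate ratio is the same at all covariate levels. Protocol Chapter 2 reports a reduction of about 25% at 1–5 months and 14% overall in the earlier trial, so a common ratio across age mixes is not assured.

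Fourth, the SAP already has an age-adjusted model. It is secondary and at individual level, has no MUAC or stratum term, and leaves the primary interval as it is.

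Fifth, timing. SAP version 1.6 is dated February 2023, after the month-36 window of February to July 2022 in Protocol 4.2. Protocol 15.5 has the study biostatistician prepare by-arm Closed Reports, and SAP 2.2 has the trial biostatistician run the interim analysis. Someone who has seen arm-level data should not choose the primary model. This stands and limits the fix.

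**Conclusion.** The point holds as a recommendation to improve precision. Arm is the only predictor in the primary model; about 49% of the design variance is between communities; and age and MUAC are recorded before dosing in every community. Adjustment could narrow the primary interval at no data cost. Under assumed R² of 0.1 to 0.3 the gain is 2 to 6 points of power, and it is nil if the covariates do not predict community mortality. The figures rest on the SAP's planning inputs, 341 communities and three years of person-time with 10% loss taken as a factor of 0.9.

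The documents do not support reading this as a flaw in validity or as a shown loss of power.

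**What to change.** In SAP 2.1.1, prespecify an adjusted negative binomial model with treatment arm and three fixed terms: month-0 community mean MUAC, month-0 share of listed children under 12 months, and HDSS stratum. Take the P-value by permuting arm within HDSS stratum, as randomized under SAP 4, with the covariates held fixed. Keep the unadjusted rate ratio as a named analysis for comparison with the earlier trial. State that the two ratios have the same estimand only under a common rate ratio.

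Make the adjusted model primary only if staff masked to arm-level results fix it, and record when and by which role in the revision history. Otherwise list it as a named supplementary analysis, in which case the primary interval stays as planned.

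The cost is SAP wording and minor programming. No new data are needed.

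Separately, reconcile 278 with 341 communities, since power depends on which is right.

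### The Poisson refit at an aggregation parameter of 30 can make a model-based rate-ratio interval up to about 12% too narrow near the threshold; the interval method is not stated (minor)

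*SAP*

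**What the plan says.** SAP section 2.1.1 takes the number of deaths per community as the outcome and fits negative binomial regression with treatment arm as a community-level predictor. Under its statistical considerations it sets a switch: "For negative binomial regression, an aggregation parameter of 30 or greater will cause us to re-fit using Poisson regression". It gives no reason for the value 30 and does not define the parameter.

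The test does not rest on the model's standard error: "The statistical significance assessed by permutation testing at the level of the randomization unit", and again "Statistical tests will be conducted with Monte Carlo permutation based on the randomization unit".

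The SAP does not say how the confidence interval for the rate ratio is obtained, nor that the refitted Poisson model has standard errors robust to community clustering. Where it wants clustering in other models (the secondary individual-level Poisson regression by age, and the MUAC and malaria analyses), it says so.

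A general model check by residuals or goodness of fit, to be used where needed, ends with: "Inadequate model fit will prompt us to report alternative models".

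For planning, SAP section 3 states "We assume the same coefficient of variation for village-level mortality as for the Niger site, i.e. 0.34" and "The base rate for mortality is assumed to be 0.02 per year in the target age range".

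**The concern.** A switch from negative binomial to plain Poisson does no harm only if the overdispersion left at the switching point is negligible for the counts in hand. That depends on the mean count as well as on the parameter, because the variance is inflated by 1 + mean/parameter. A parameter of 30 would be close to Poisson for counts of one or two. With about nine deaths per community it is not.

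At stake is the precision reported beside the primary rate ratio. A Poisson interval that ignores the remaining between-community variation could exclude 1 while the permutation p-value does not reject. The switch also brings little in return, since the negative binomial fit approaches Poisson by itself when overdispersion is absent.

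**Working it through.** **Inputs** (SAP section 3 unless noted): control rate 0.02 per year; reduction 0.1365, so treated rate 0.02 × 0.8635 = 0.01727; CV 0.34; 16.7% of 1000 people, so 167 children per community; 10% loss per year; three years (SAP 2.2); 341 communities. The aggregation parameter is taken as the negative binomial size θ, with variance μ + μ²/θ. This is an assumption, but under the inverse definition the rule would move to Poisson when overdispersion is extreme, which makes no sense.

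**1. The plan's own figure.** The SAP does not state person-years per cluster. With y = 167 × (1 + 0.9 + 0.81) = 452.6, its formula gives

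c = 1 + (1.960 + 0.842)² × [0.03727/452.6 + 0.34² × (0.02² + 0.01727²)] / 0.00273² = 172.7 per arm,

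against the stated 170. Power with 170.5 per arm is 79.5%, against 80%. This is close enough to rely on the inputs.

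**2. Deaths per community.** Control 0.02 × 452.6 = 9.05; treated 0.01727 × 452.6 = 7.82; mean 8.4.

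**3. What 30 means.** CV = 1/√30 = 0.183. The planned CV of 0.34 corresponds to θ = 1/0.34² = 8.65.

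**4. Cost of the refit if the interval is model-based.** Standard error ratio = √(1 + μ/θ); Poisson interval coverage = 2Φ(1.96/ratio) − 1.

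| θ | μ | Variance ratio | SE ratio | Poisson interval too narrow by | Coverage |
|---|---|---|---|---|---|
| 30 | 9 | 1.30 | 1.14 | 12% | 91.4% |
| 30 | 8.4 | 1.28 | 1.13 | 12% | 91.7% |
| 50 | 8.4 | 1.17 | 1.08 | 7.5% | 93.0% |
| 100 | 8.4 | 1.08 | 1.04 | 4% | 94.0% |
| 300 | 8.4 | 1.03 | 1.01 | 1.4% | 94.7% |

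Other readings of the loss assumption (407 to 501 person-years) move the figure at θ = 30 to between 10.7% and 12.7%. If the census index in SAP 2.1.1 (0 to 3) were taken to mean about two years, control deaths would be about 6.4 to 6.7 and the shortfall about 9 to 10%. Testing the final analysis at 0.049 instead of 0.05 does not change the width ratio.

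**5. How often the rule fires, and with what effect.** Simulated gamma-Poisson counts in 341 equal-sized communities; 3,000 trials per row, except 1,500 for the last two rows.

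| True CV | Rule fires | Poisson coverage when it fires | Negative binomial, same trials |
|---|---|---|---|
| 0.34 (planned) | 0% | – | – |
| 0.20 | 33% | 91.1% | 94.9% |
| 0.183 | 55% | 91.7% | 94.6% |
| 0.15 | 86% | 93.2% | 95.4% |
| 0.10 | 99% | 95.0% | 96.1% |
| 0 | 100% | 95.3% | 95.6% |

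Monte Carlo error is about 0.9 points in the 0.20 row and 0.7 in the 0.183 row. With community sizes varying (size CV 0.6, an assumption; 1,500 trials), the figures at a true parameter of 30 were 92.4% against 95.0%. At a true parameter of 20 the rule fired in only 11% of trials. In those (about 165 trials) Poisson covered 84 to 87% and negative binomial only 89 to 90%, because these are trials in which dispersion happened to be underestimated. Averaged over all trials, fired or not, the rule covered 92.6 to 95.5%.

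**6. The test.** Permuting communities with the Poisson rate ratio as statistic gave a type I error of 4.7 to 5.2% at θ = 30 and 4.2 to 4.5% at θ = 8.65 (2,000 trials each). A Poisson Wald test would have given 8.4 to 9.7% and 16 to 20%.

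**7. Sparser models at the planned CV of 0.34.** The rule fires by chance in about 1 to 2% of year-1 analyses, 12% of single-phase analyses (about 1.5 deaths per community) and 6 to 8% of age-group analyses with about 2 deaths per community. In those trials the two models had identical coverage (single phase 95.1% each; two deaths 91.3% each; year 1 83.3% each, on only about 36 trials). When the rule fires on sparse data the estimated parameter is usually very large, so the two fits coincide.

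**The case against.** Four arguments can be made for leaving the rule alone.

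- **No interval method is stated, so none is shown to be wrong.** This stands as far as it goes: the loss of coverage is conditional on a model-based interval. But nothing in the SAP makes the refitted Poisson model cluster-robust, and the silence is itself a gap.
- **The rule is dormant under the plan.** This stands for the 36-month primary model. The CVs of 0.15 to 0.20 at which it bites are not in the documents. The 0.34 is borrowed from another country, however, and the rule was written for the case where it proves too high.
- **The model check would catch it.** At θ = 30 the Pearson statistic per degree of freedom is about 1.28 on 339 degrees of freedom (p about 0.0004). A 5% Pearson check flagged 95%, 89% and 68% of fired trials at CV 0.20, 0.183 and 0.15. If negative binomial were then reported, overall coverage would be 94.4 to 94.9%. But the check is discretionary, names no test, and adds alternative models without overriding a mandatory refit.
- **The remedy has limits of its own.** This stands in part. A negative binomial interval can also disagree with a permutation p-value, and a fallback on non-convergence is also data-dependent. With robust standard errors, though, that fallback does not cost coverage.

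Three stronger readings are tempting and are not supported. A reader might infer that intervals are too narrow whenever the rule fires; step 4 shows the shortfall fading, and with no overdispersion the rule always fires and the Poisson interval is right. A reader might infer that the primary test is compromised; it is a permutation test and holds its level (step 6). A reader might infer that chance firing in the year-1, phase and age-group models does harm; there the two models give practically the same interval (step 7).

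**Conclusion.** The concern holds as a minor point. At the stated threshold and the planned number of deaths, plain Poisson leaves out overdispersion that is not negligible: a variance ratio of 1.28 to 1.30, an interval up to about 12% too narrow, and coverage of about 91 to 92%. In the simulations at CV 0.15 to 0.20 negative binomial did better in the trials where the rule fired, and in none of the scenarios was the refit better.

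This rests on three conditions: the aggregation parameter is the size parameter, the interval is model-based, and the true between-community CV is nearer 0.15 to 0.20 than the planned 0.34. The primary p-value is unaffected.

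**What to change.** Preferred: delete the refit sentence in SAP 2.1.1 and report the negative binomial rate ratio and interval whatever the estimated aggregation parameter. Use Poisson with community-robust standard errors only if the negative binomial fit does not converge. In a smaller simulation (400 to 500 replicates) that robust Poisson interval covered 94% at CV 0.20 and 0.183.

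Alternative: keep the rule, define the aggregation parameter, and state that the Poisson interval is community-robust or obtained by inverting the permutation test.

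In either case, name the method for the rate-ratio interval. The cost is one SAP sentence and a revision-history entry, with no new data and no change to the primary test. Where the rule would have fired with some overdispersion present, the reported interval becomes slightly wider.

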Verbal autopsy will be conducted in the district according to current methods for measuring verbal autopsy for all children aged 1-59 months who died during the study.³ The interview is conducted with the caregivers or relatives, using the WHO standard verbal autopsy questionnaire WHO-VA-2016. The interview usually takes place two months after the event with the person who assisted the deceased before the death. The data collected will be coded using InterVA 4.

Treatment

Children aged 1-59 months on the current census will be offered weight- or height-based (<1 year and older children who can't stand will be weighted; ≥1 year will be measured with a flexible dosing stick), directly observed, oral azithromycin suspension (or oral placebo) every 6 months for 3 years as performed in trachoma programs. Specifically, individuals are eligible on or after their one month birthday, and prior to the day of their fifth birthday.

At the final treatment distribution, CHAT 36, all children 1-59 months old will be given a single dose of azithromycin. Placebo will not be utilized at the final phase.

Antibiotic Coverage Surveillance

We will estimate antibiotic coverage from the most recent biannual census records. At the end of each treatment round at months 6, 12, 18, 24, and 30 we will identify any children who have missed 2 or more consecutive treatments, and forward this information to the census team.

Birth history at the 36 months visit

At the final visit (36 month) we will obtain birth history in a subset of communities. All women in childbearing age living in selected communities will be asked if they experienced births in the last 10 years. Name of women, age, name of children and age or date of birth will be collected. Vital status of each birth will be recorded.

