12.5 Antibiotic Distribution & Monitoring Coverage

After the MORDOR 0 census and monitoring/collection is complete, treatment (azithromycin and placebo) will be administered to all eligible community

members per study protocol. Teams will participate in training exercises regarding drug/placebo distribution and recording techniques prior to each treatment cycle. Training will be in accordance with the Zithromax Program Manager's Guide from the International Trachoma Initiative.

During mass drug administration, distribution team members will use tablet computers equipped with an electronic data capture system to seek out each eligible child on the census, administer antibiotic or placebo, and record whether or not each person has been treated. The distribution team will document individual reasons for not being treated (e.g. death, temporary absence, permanent migration, refusal of treatment, etc.). Consumption of medication will be directly observed and the dose distributed will be documented in the electronic data capture system.

We will estimate antibiotic coverage from the most recent biannual census records, aiming for treatment of 80% of children. At the end of each treatment round, the DCC will identify any children who have missed 2 or more consecutive treatments, and relay this information to the study coordinator. Census teams will discern the reason for missing treatments (including unrecorded death) at the next scheduled census. This system will serve as a quality control mechanism to reduce the number of false negative deaths in the study.

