- Individual level missing data (due to loss to follow-up or dropouts) is expected. If an individual is lost to follow-up or otherwise unavailable during an interval of length D , then the individual will not be assigned any amount of person time. If an individual dies within an interval of length D , then the individual is assumed to contribute the amount of person-time $D/2$ to the denominator (midpoint imputation).
- Village-level missing data could occur for various reasons, including field error, withdrawal of support from village leadership, or other unforeseen reasons. The analytic

plan will be to analyze all available information (including data from any community prior to the time of dropout of that community). If a community drops out and then re-enters, all available data (before and after the dropout period) will be analyzed.

Supplementary analyses.

The purpose of the supplementary analyses reported in this section is to assess the role of statistical choices and data quality choices in shaping the result.

survival Cox proportional hazard regression of time to death, with inference based on permutation test of randomization unit

Secondary analyses of mortality.

All secondary analyses will be sharply distinguished from the primary prespecified analysis and will be identified as such. Secondary analyses include outcome variables or planned subsets which contribute either additional insight or address different scientific questions than the primary analysis.

age Poisson regression at the individual level, clustering on community, including age as a covariate (we will both adjust for age, as well as examine age-treatment interactions)

age Negative binomial regression, reporting using the same age categories as in MORDOR Niger/Malawi/Tanzania (1–5 months, 6–11 months, 12–23 months, 24–59 months)

timing Cramer–von Mises comparison of death time conditional on mortality, between arms; comparison of death time density between arms

the number of azithromycin doses received Logistic regression at the individual level, clustering on community, using the number of azithromycin doses as the primary predictor

factorial analysis Logistic regression at the individual level, clustering on community, using the interaction term for the two factors, the community and individual arms

Additional secondary outcomes.

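### The planned regression of death on azithromycin doses received gives a false protective gradient, because a child must survive to be dosed again

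*SAP*

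**What the plan says.** SAP 2.1.1, under the secondary analyses of mortality, specifies a logistic regression on individual children, with clustering by community, "using the number of azithromycin doses as the primary predictor". The line gives no person-time, interval structure, time-updating of exposure, landmark or age term. It does not say whether placebo children enter with a count of zero.

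The primary model differs: it uses person-years, and "the treatment variable is a community level variable, not an individual level variable".

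Protocol 5.1.1 offers eligible children "directly observed, oral azithromycin suspension (or oral placebo) every 6 months for 3 years", which means masked rounds at months 0, 6, 12, 18, 24 and 30. It then adds a dose in both arms: "At the final treatment distribution, CHAT 36, all children 1-59 months old will be given a single dose of azithromycin". Protocol 12.5 has distribution teams "record whether or not each person has been treated", with death among the listed reasons for non-treatment. On interpretation, the SAP promises only that "All secondary analyses will be sharply distinguished from the primary prespecified analysis and will be identified as such".

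**The concern.** The number of doses a child has received depends on how long the child lived and stayed in the cohort. Setting that count against death treats a result of survival as though it were an exposure. Three further features push in the same direction:

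- Follow-up differs between children (one interval to six), and logistic regression ignores this.
- Mortality falls with age (Protocol, Chapter 2), and the youngest children have had the fewest rounds.
- Children under 3.8 kg are not dosed but stay in the outcome (Protocol, Eligible Individuals), so a count of zero partly marks frail infants.

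An inert drug would therefore appear to protect, more strongly with each dose. If the primary result were borderline, a highly significant prespecified gradient could be taken as corroboration.

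**Working it through.** **1. The plan's own figure.** The SAP states no figure for this analysis. The primary sample size was reproduced first, to confirm the inputs. With λ0 = 0.02, λ1 = 0.02 × (1 − 0.1365) = 0.01727, k = 0.34 and y = 167 × 3 × 0.9 = 450.9 person-years:

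c = 1 + (1.960 + 0.842)² × [(0.03727/450.9) + 0.1156 × 0.000698] / 0.00273² ≈ 173 per arm, against 170 stated. This is within 2%.

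**2. The mechanism by hand.** With six rounds and a constant 2% yearly hazard, a child with six doses can die only in the last half-year: 1 − exp(−0.02 × 0.5) = 1.0%. In a simple open-cohort null simulation (80% coverage, constant hazard), risk of death in the azithromycin arm by 0 to 6 doses was 6.8, 6.4, 5.3, 4.0, 2.5, 1.5 and 1.0%. It was 4.0% in the placebo arm. The drug does nothing here; survival time alone produces the slope.

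**3. Null simulation with the SAP's inputs.** From SAP 3: 341 communities, 167 children each (1000 × 16.7%), 2% yearly mortality, coefficient of variation 0.34, 10% yearly loss. From Protocol 12.5: 80% coverage. Assumed, because the documents give no figures: birth inflow, exits, and relative hazards of 3.0, 2.0, 1.2 and 0.55 for ages under 6, 6–11, 12–23 and 24+ months in the age-graded scenario. The model was logistic, with one record per child and community-clustered standard errors. Odds ratios per dose:

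| Scenario (no drug effect) | Azithromycin arm only | Both arms, placebo = 0 masked-round doses |
|---|---|---|
| Closed cohort | 0.26 | 0.83 |
| Open, constant hazard, no loss | 0.72 | 0.88 |
| Open, constant hazard, 10% loss | 0.77 | 0.90 |
| Open, age-graded hazard, 10% loss | 0.62 | 0.82 |
| Open, constant hazard, 10% loss, month-36 dose counted in both arms | 0.69 | 0.79 |

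Every dataset in every row gave an odds ratio below 1 with p < 0.05. For both arms with loss, z ≈ ln(0.897)/0.0130 = −8.4 (constant hazard) and ln(0.817)/0.0141 = −14.3 (age-graded).

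**4. Scale.** In a log-linear model, six doses against none would show 0.90⁶ = 0.53 to 0.82⁶ = 0.30, an apparent 47% to 70% reduction in odds. The trial is designed around 13.65%.

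**5. Negative control.** In the simpler simulation, placebo doses within the placebo arm gave null odds ratios of 0.62–0.72 per dose. Azithromycin doses within the azithromycin arm gave 0.61–0.72.

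**6. Child-interval records.** In the azithromycin arm, with doses counted to the start of each interval but no age term, the null odds ratio was 1.00 under a constant hazard and 0.78 under the age-graded one. Adding age bands gave 0.999, 0.999 and 1.002 in three scenarios, with p < 0.05 in 2.5–7.5% of 40 datasets each. A child-interval Poisson model with an arm-by-treatments-received term and age gave a rate ratio of 0.99 with no false positives in 24 runs. A separate set of six runs of the arm-by-treatments Poisson model averaged 1.003.

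**The case against.** The strongest reply is that the SAP defines neither the record nor the counting window. The trial is organized in census-to-census intervals, so the authors may have meant one record per child-interval with doses counted beforehand, and immortal time then disappears. That is possible, but it does not rescue the text. No age term is stated, mortality falls with age, and the null odds ratio is then still 0.78 per dose in the azithromycin arm under the assumed gradient. One record per individual is also the more natural reading of the line.

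Several limits do stand:

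- The within-arm odds ratios illustrate the mechanism; the SAP does not restrict the analysis to one arm, so the both-arm column is the relevant one.
- The size of the bias depends on assumed age-specific hazards, births and exits. The documents support only the direction of the age effect.
- This is one secondary analysis, and the SAP undertakes to label it so. Labelling does not remove bias. How readers would use the result is a judgement.
- SAP version 1.6 is dated February 2023, after the last visit window in the protocol schedule (July 2022), so a change now must be logged and justified.

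**Conclusion.** The concern holds. As written, the analysis makes the exposure depend on survival and will tend to show protection when there is none. With both arms included and month-36 doses left out, the null odds ratio per dose is about 0.82–0.90 in open cohorts, significant in every simulated dataset; counting the month-36 dose takes the constant-hazard figure from 0.90 to 0.79. Late entry, ageing out and loss to follow-up weaken the bias but do not remove it, and its direction was the same in every one-record-per-child scenario. The exact size rests on the assumed hazards and cohort flows. The primary analysis and the sample size are not affected. The line should be corrected before any dose-response result is reported.

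**What to change.** Replace the line with a child-interval Poisson or Cox model that includes:

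- as predictor, the number of treatments received up to the start of the interval, updated at each interval;
- arm, and an arm-by-treatments-received term as the quantity of interest, so that placebo recipients with the same count of masked treatments are the comparator;
- adjustment for age, with person-time included and clustering on community.

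The text should also settle three definitions. First, whether the round that opens an interval counts: a child who dies between census and distribution cannot receive that dose, so if it counts, time at risk should start at distribution. Second, that the month-36 dose is excluded, which follows automatically when only earlier treatments are counted. Third, whether the individually randomized infant dose (Protocol 5.3) is counted.

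The cost is a dated entry in the SAP revision history and some programming; treatment status is already recorded in both arms at each round. If the existing model must be kept because it was prespecified, report it beside the new one, with its null bias stated and the same model on placebo doses as a negative control. Receipt of treatment is not randomized, so the new analysis should still be labelled exploratory.
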